### 13.4 Reproductive history

Participants will be asked if they are currently trying for children. Infertility will be defined as failure to achieve a clinical pregnancy after 12 months or more of regular unprotected sexual intercourse (Zegers-Hochschild et al. 2009).

Participants will be asked if they have tried for children in the past, and if so:

- Number of pregnancies
- Number of children
- Number of miscarriages
- Have they been seen in the fertility clinic?
- Have they required any fertility treatment?
- Have they developed gestational diabetes?
- Have they developed pre-eclampsia or any pregnancy related complications?

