## 8. Study aims

Primary outcome:

- To examine if OSA is associated with impaired QoL in women with PCOS.

Secondary outcomes:

- To assess the relationship between OSA and body composition, hirsutism (modified Ferriman-Gallwey score), period cyclicality, reproductive outcomes, insulin resistance (HOMA-IR), hyperandrogenism, depression and anxiety, FPG, glycated haemoglobin (HbA1C), reproductive hormone profile, lipids, and inflammation (high sensitivity C-reactive protein, hCRP) in women with PCOS.

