### 14.2 Statistical analysis

Continuous baseline characteristics for each of the PCOS OSA and PCOS low risk OSA groups will be summarised using the mean ( $\pm$ SD) and the median (interquartile range). If the data are approximately normally distributed, the means for the two groups will be compared using the independent t-test. If the data are not normally distributed, the two groups will be compared using the Mann-Whitney U test. Data will be checked for normality using the Shapiro-Wilk test (Razali and Wah 2011). Categorical baseline characteristics for each of the PCOS OSA and PCOS low risk OSA groups will be summarised by reporting the count and percentages in each category. The two groups will be compared using the chi-squared test.

To compare quality of life for the PCOS OSA and PCOS low risk OSA groups, we will fit linear models for each of the primary outcomes of interest (domain scores on the PCOSQ and WHOQOL-BREF questionnaires). The dependent variable in a linear model will be a primary outcome and independent (predictor) variable of interest will be whether a woman is from the PCOS OSA or PCOS low risk OSA group. As the groups may be imbalanced in other predictors for the primary outcomes, the models will adjust for potential confounders such as age, BMI, WHR, use of oral contraceptive pill, ethnicity, education level, marital status, other ongoing illnesses, and parity. Data will be assessed if they are approximately normally distributed; and if they are not, they will be transformed, for example, by taking the logarithm of the outcome variables.

Correlations will be evaluated using Pearson's coefficient (or Spearman's coefficient for non-normally distributed data). A two tailed P value of <0.05 will be considered statistically significant. Statistical analysis will performed using the SPSS statistics package (SPSS Inc., Chicago, USA).

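### Pregnancy, birth and miscarriage counts are asked only of women who say they have tried for children, although parity is a named covariate and reproductive outcomes are a secondary outcome

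*Combined protocol and SAP*

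**What the plan says.** Section 13.4 first asks whether the woman is trying to conceive now and defines infertility. It then sets a filter, "Participants will be asked if they have tried for children in the past, and if so", and lists seven items below it. Four kinds of item matter here: "Number of pregnancies", "Number of children", "Number of miscarriages", and the complication items (gestational diabetes, and "Have they developed pre-eclampsia or any pregnancy related complications"). The other two items concern attendance at a fertility clinic and fertility treatment. Nothing is listed for a woman who answers no to the filter.

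Two parts of the plan use these data. Section 14.2 fits linear models to the PCOSQ and WHOQOL-BREF domain scores and gives examples of the confounders to adjust for, ending with "ethnicity, education level, marital status, other ongoing illnesses, and parity". Section 8 includes reproductive outcomes among the secondary outcomes.

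Section 12 says that participants give a full medical history and answer detailed questions on fertility, and Table 2 marks medical and reproductive history for all participants. Neither place names pregnancy or parity as an item.

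**The concern.** Having tried for children is a sensible filter for fertility clinic attendance and fertility treatment. It is the wrong filter for pregnancies, births, miscarriages and complications, which happen whether or not the pregnancy was intended. Two analyses are exposed.

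First, parity is a candidate covariate in the primary models, and the question that supplies it is not put to everyone. The plan has no rule for missing covariates and does not say how parity is coded when the list is skipped. The analyst would have to choose between losing women and entering an assumed value.

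Second, pregnancy counts, miscarriages and complications would be compared between the OSA and low-risk groups only among women who report having tried. Women who conceived without trying are left out of a comparison that concerns what happened in pregnancy.

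**Working it through.** **Inputs.** The filter and item list come from section 13.4, the covariate list from section 14.2, the secondary outcomes from section 8, the other history-taking from section 12 and Table 2, and the sample size from section 14.1. The share of women who never tried, and the share who gave birth without trying, are not given anywhere.

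**Step 1: is there an unfiltered source?** The medical history and fertility questions in section 12 are not itemised; the reproductive questions are itemised only in section 13.4. The appendix holds the hirsutism score, the ESS and the Berlin questionnaire, none of which asks about pregnancy. So no unfiltered source is named.

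**Step 2: what the filter does to each kind of woman.**

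| Ever tried in the past | Obstetric history | Recorded under 13.4 | Blank kept as missing | Blank set to zero |
|---|---|---|---|---|
| Yes | Any, including unplanned pregnancies | Full counts | Kept, parity right | Kept, parity right |
| No | Never pregnant | Nothing | Lost if parity is in the model | Parity right |
| No | Pregnant, no birth | Nothing | Lost if parity is in the model | Parity right; pregnancies and losses unrecorded |
| No | At least one birth | Nothing | Lost if parity is in the model | Parity wrong; pregnancies and complications unrecorded |

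The two ways of handling the blanks affect different groups. Missing values remove everyone in the last three rows. Zero coding misclassifies parity only in the last row. In both cases the last two rows are absent from the comparison of pregnancy outcomes. A woman trying now for the first time could fall on either side of the filter, because the question refers to the past.

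**Step 3: how much slack the sample has.** The plan's own figure is 38 women (15 and 23) for 80% power at effect size 0.98, two-sided 5%. For a two-sample t-test the noncentrality is d × √(n1·n2/(n1+n2)) = 0.98 × √(15 × 23/38) = 2.95 on 36 degrees of freedom, which gives power of 81.9%. The plan's figure therefore reproduces. At about the same 40/60 split, 37 women (15/22) give 81.2% and 36 women (14/22) give 79.5%. The planned size can lose one woman and stay above 80%, but not two.

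This is the power of the unadjusted comparison used in section 14.1. That comparison does not use parity and would lose nobody for a blank parity field. The step shows only that the sample has little to spare. It does not measure the loss in the adjusted models.

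**The case against.** The strongest reply is that section 13.4 is a short narrative and not the case report form, which is not among the documents. A full medical history is taken from every participant, and a clinician taking one may well record pregnancies. This stands as a reason to say that data may be lost, not that they will be. It does not remove the gap, because the only written instruction on these items is the filtered one.

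Three stronger readings are tempting, and the documents do not support them:

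- A reader might infer that every woman with only unplanned pregnancies is skipped. The filter asks whether she ever tried, not whether her pregnancies were planned. A woman with unplanned pregnancies who tried at another time passes it, which is plausible in a condition that the protocol links to subfertility.
- A reader might infer a number of affected women and a resulting fall in power. Any such number needs the share of women who never tried (for missing values) or who gave birth without trying (for zero coding). Neither is given, and one assumed share cannot serve for both.
- A reader might infer that parity enters every primary model. Section 14.2 offers its covariates as examples, and parity is one of nine.

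**Conclusion.** The point holds in a limited form. Followed as written, section 13.4 leaves parity unrecorded in women who have never tried for children, while section 14.2 names parity as a potential confounder. It also confines pregnancy counts, miscarriages and complications to women selected on intention to conceive.

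The size cannot be calculated from the documents, nor can the direction of any bias between the two groups. The effect on the primary comparison is probably modest, since parity is one of several example covariates. The effect on the pregnancy-related part of the secondary outcomes is more direct, because there the filter decides who is in the comparison. The conclusion assumes that the case report form follows section 13.4 and that the medical history does not fill the gap. This is a cheap improvement and does not threaten the study's validity.

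**What to change.** In section 13.4 and on the case report form:

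- Ask every participant for the number of pregnancies, births and miscarriages, and ask about gestational diabetes, pre-eclampsia and other pregnancy complications.
- Keep the question on having tried for children as the filter only for the infertility, fertility clinic and fertility treatment items.

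In section 14.2:

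- State that parity is taken from the number of births, and that never-pregnant women are coded as zero.
- State that pregnancy complications are compared among women who have ever been pregnant.

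The cost is a small change to the question order and about a minute more in a visit planned at roughly 1.5 hours. No new procedure or instrument is needed.

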### 13.5 Clinical history

**Period cyclicity:** Women will be asked to estimate how many periods they had in the four months preceding the study visit. We accept that there is a risk of recollection bias with this method. For participants using hormonal contraception, this information will not be collected.

**Hirsutism:** This will be assessed using the modified Ferriman-Gallwey score (Appendix). The modified Ferriman-Gallwey scoring system (Ferriman and Gallwey 1961) is a useful clinical tool, though subjective, in assessing hirsutism. Women are asked to assess the degree of their body hair using pictures of nine body areas and to give a score ranging from 0 (absence of terminal hair growth) to 4 (heavy terminal hair growth) for each area. A total score of 8 or more on the modified Ferriman-Gallwey scoring system is widely considered suggestive of hirsutism (DeUgarte et al. 2006).

**Risk of OSA:** The risk of OSA will be assessed as per clinical practice using the Berlin and ESS questionnaires. Although the ESS (Appendix) is commonly used, it mainly assesses sleepiness (Johns 1991). A score of more than 10 on the ESS is consistent with excessive daytime sleepiness. The Berlin questionnaire (Appendix) assesses the risk of OSA and has a sensitivity of around 85% (Netzer et al. 1999).

### 13.6 Quality of life

QoL will be assessed using the PCOS health-related quality of life questionnaire (PCOSQ), and the World Health Organisation QoL questionnaire (WHOQOL-BREF). We will not be using an OSA disease-specific QoL questionnaire as only a proportion of study participants will have OSA and subsequently such a questionnaire will not reflect the QoL in controls well.

The PCOSQ (Cronin et al. 1998) is a validated method of assessing QoL in women with PCOS. It is the only PCOS condition-specific measure of QoL. The PCOSQ includes 26 items (questions) to cover 5 domains which were found to be of most importance to women with PCOS: emotions (8 items),

body hair (5 items), weight problems (5 items), menstrual problems (4 items) and infertility (4 items). Each item is scored out of 7, in which a score of 7 denotes no problems or difficulties and a score of 1 indicates maximum impairment. Each domain score is calculated by dividing the total score of all items within a domain by the number of items in that domain. The PCOSQ takes 10–15 minutes to complete and lower scores suggest impaired QoL. The PCOSQ has been found to demonstrate acceptable internal consistency (0.70–0.97) and test-retest reliability (Malik-Aslam et al. 2010). A difference of 0.5 on the 1 to 7 scale has been suggested to represent the minimal important difference in the questionnaire score, i.e. the smallest change in score that women feel is important in their daily lives (Cronin et al. 1998).

The WHOQOL-BREF (Skevington and McCrate 2012) is a validated generic measure of QoL. It includes 26 questions to assess four major domains (subscales): physical, psychological, social and environment. Scores are given out of a hundred and higher scores are better; a score of more than 50% indicates an acceptable to good QoL. The WHOQOL-BREF has been shown to display high internal consistency (0.92); good test-retest reliability (0.66 – 0.72); discriminant validity (discriminating sick from healthy people), and content validity (correlation with the Short Form 36 Health Survey (SF-36)) (Skevington and McCrate 2012). WHOQOL-BREF provides a very good holistic assessment of QoL in the general population and its validation study included a group of women with PCOS, and a group of people with sleep disorders (Skevington and McCrate 2012).

### **13.7 Depression and anxiety**

Depression and anxiety will be assessed using the Hospital Anxiety and Depression (HAD) scale. Participants on antidepressant medications will be considered as having ‘clinical depression’.

The HAD scale (Zigmond and Snaith 1983) is an internationally validated (Herrmann 1997) method of assessing patients’ mood. It consists of 14 items (questions), seven reflecting anxiety and seven reflecting depression. Each question answered will give the patient a four point (0 – 3) response category with the possible scores range from 0 to 21 for anxiety and 0 to 21 for depression. A score of 0 to 7 in each sub-scale is regarded as normal while a score of 11 or higher indicates probable presence of mood disorder. The HAD scale takes 3 – 5 minutes to answer and the patient is asked to choose the answer which best reflects how they felt in the last week.

### **13.8. Sleep studies**

The diagnosis of OSA will be made using portable home-based sleep machines (Alice PDx, Philips, US). Alice PDx is a small, portable, easy to use and validated device for the diagnosis of OSA. The device is connected to a nasal cannula to measure patient airflow; pulse oximeter to measure oxygen saturation; and two belts applied around the chest and abdomen to measure chest and abdominal wall movements. The device also has an indicator which displays how many hours of good quality data were obtained. The study doctor will explain to the patient how to use the device and the patient needs to wear the device before going to bed. The analysis of the sleep study data will be performed by [name] or a sleep technician. Patients with confirmed diagnosis of OSA on sleep studies will be followed up in the chest clinic as part of NHS routine care.

## 14. Statistical considerations

### 14.1 Sample size calculation

The QoL between the two groups will be compared based on the PCOSQ and the WHOQOL-BREF questionnaires.

The validation study for the WHOQOL-BREF (Skevington and McCrate 2012) included a group of people with sleep disorders and a group of healthy controls. Based on this study a total sample size of 38 participants will give us 80% power, and 5% significance (two-tailed), to detect a mean difference of 17.8 on one item of the WHOQOL-BREF (large effect size 0.98) between cases (PCOS OSA) and controls (PCOS low risk of OSA), **Table 3**. We used an allocation ratio for cases/controls of 0.67, 40% of participants in the PCOS OSA group, and 60% in the PCOS low risk OSA group. Sample size was calculated using GPower 3.1.

	Well n=141		Sleep disorders group n=45		Pooled SD	Mean difference	Effect size	n/ PCOS OSA group	n/PCOS low risk OSA group	Total sample
Item	Mean	SD	Mean		SD					
Physical Health	75.41	18.72	57.65	17.67	18.2	17.8	0.98	15	23	38

**Table 3.** Difference in WHOQoL-Bref scores on the physical health item between people with sleep disorders breathing and healthy controls (Skevington and McCrate 2012).

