## 5. Summary

**Background:** Polycystic ovary syndrome (PCOS) is the most common endocrine disorder in women of reproductive age. PCOS is associated with multiple co-morbidities including obesity, insulin resistance, subfertility, impaired quality of life (QoL) and increased risk of type 2 diabetes. Obstructive sleep apnoea (OSA) is a common medical condition that is often undiagnosed, particularly in women. Obesity is a common risk factor for OSA and PCOS and OSA is associated with comorbidities similar to those observed in patients with PCOS such as insulin resistance, increased risk of type 2 diabetes, and impaired QoL. Hence it is not surprising that OSA and PCOS might co-exist.

However, the impact of OSA in women with PCOS remains unclear and understudied. It is plausible that OSA may contribute to the subfertility and impaired QoL observed in women with PCOS by increasing insulin resistance, activation of the sympathetic nervous system, disturbing the hypothalamic/pituitary/ovarian axis, and contributing to excessive daytime sleepiness and reduced mood.

**Hypothesis:** Women with PCOS and OSA, compared to women with PCOS only, have more severe clinical and biochemical features of PCOS and impaired QoL.

**Study design:** Observational cross-sectional study.

**Setting:** A secondary care PCOS clinic in the WISDEM Centre, University Hospital Coventry.

**Study outcomes:** The primary aim of this study is to examine the relationship between OSA and impaired QoL in women with PCOS. Study secondary outcomes are to examine the relationship between OSA and the clinical and biochemical features in women with PCOS.

**Methods:** 38 women with PCOS will be recruited from the PCOS clinic. Women with increased risk of OSA, based on the Berlin questionnaire and the Epworth Sleepiness Scale (ESS), will have home-based sleep studies performed. They will also be referred to the Respiratory Physician, as part of routine NHS care.

Study participants will be divided based on the results of the Berlin and ESS questionnaires and sleep studies into two groups: 1) PCOS low risk OSA: women with normal ESS and normal Berlin questionnaire (no sleep studies performed), or women with normal sleep studies; and 2) PCOS OSA: women with OSA proven by sleep studies.

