### 6.1 Polycystic Ovary Syndrome

PCOS is a common disorder with a prevalence of 6 – 15% of women of reproductive age (Azziz et al. 2004; Knochenhauer et al. 1998; Diamanti-Kandarakis et al. 1999; Asuncion et al. 2000; Fauser et al. 2012). The Rotterdam criteria (Rotterdam 2004) define PCOS by the presence of two of the following three components: hyperandrogenism, oligomenorrhoea /anovulation, and polycystic ovaries on ultrasound. Oligomenorrhoea is defined as a mean cycle length > 35 days (usually fewer than nine cycles per year), while amenorrhoea is defined as cessation of menses for > 6 months (Broekmans et al. 2006). Hirsutism, excess body hair, is a common feature in women with PCOS. Polycystic ovaries (PCO) on ultrasound are defined as either 12 or more follicles measuring 2–9 mm in diameter in one of the ovaries, or an ovarian volume of >10 cm^3 (Rotterdam 2004). The diagnosis requires the exclusion of conditions with similar presentation including non-classic congenital adrenal hyperplasia (NC-CAH), androgen secreting tumours, Cushing's syndrome; thyroid disorders and prolactinomas.

PCOS is also associated with subfertility (West et al. 2014), obesity (Glueck et al. 2005), insulin resistance (IR) (Dunaif et al. 1989), increased risk of developing type 2 diabetes (Moran et al. 2010), depression and impaired quality of life (QoL) (Barnard et al. 2007; Hahn et al. 2005; Cinar et al. 2011). Although multiple cardiovascular risk markers are increased in in women with PCOS, the link between PCOS and increased cardiovascular morbidity and mortality remains controversial (Randeve et al. 2012).

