## 6.6 Justification for the study

PCOS and OSA are common conditions that are associated with obesity. PCOS is associated with subfertility, depression and anxiety, impaired QoL, increased risk of type 2 diabetes, and high prevalence of OSA. Hyperandrogenism and low progesterone levels are commonly seen in women with PCOS and may explain the increased prevalence of OSA. OSA is associated with disturbed sleep pattern, increased IR, disturbed hypothalamic/pituitary/ovarian axis, and sympathetic overactivity and subsequently may lead to a more severe phenotype of PCOS in affected women. Data from studies investigating the relationship between OSA and PCOS are limited by small sample size; not accounting for important confounders; and being at risk of selection bias. In addition, the effects of OSA on clinical outcomes in women with PCOS have not been investigated. Subsequently well conducted large observational studies are needed to investigate the relationship between OSA and clinical outcomes in women with PCOS. This is particularly important as OSA is a treatable condition.

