## - Participants

38 women will be recruited after fulfilling the inclusion and exclusion criteria. Study participants will be screened for OSA using Berlin and Epworth Sleepiness Scale (ESS) questionnaires and if both were normal then no further testing for OSA is required. If the score on either of the questionnaires was abnormal then home-based sleep studies will be arranged and the patient will be referred to the Respiratory Physician as per routine clinical care.

OSA will be assessed by a single overnight home-based cardiorespiratory sleep study using a portable multichannel device (Alice PDx, Philips, US) and scored in accordance with the International Classification of Sleep Disorders (ICSD-3) (American Academy of Sleep Medicine 2014). The scoring of the sleep studies will be performed by [name], Respiratory Physician, or a sleep technician. Sleep studies with <4 hours of adequate recordings will be repeated and excluded if the quality remained poor. OSA is defined by either an AHI of  $\geq 5$  with daytime sleepiness as well as gasping, choking or snoring; or an AHI of  $\geq 15$  in the absence of symptoms (American Academy of Sleep Medicine 2014).

Participants will be divided into two groups depending on the results of the ESS and Berlin questionnaires and sleep studies:

1. PCOS low risk OSA: women with PCOS with either normal scores on both the ESS and Berlin questionnaires, or who had normal sleep studies.
2. PCOS OSA: women with PCOS who had sleep studies confirming the presence of OSA.

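### Is the 80% power in section 14.1 unsupported because its 17.8-point difference comes from well people versus people with sleep disorders?

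*Combined protocol and SAP*

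**What the plan says.** Section 14.1 states that the WHOQOL-BREF validation study "included a group of people with sleep disorders and a group of healthy controls". Table 3 gives the physical health scores: well people (n=141) mean 75.41, SD 18.72; sleep disorders group (n=45) mean 57.65, SD 17.67; pooled SD 18.2, difference 17.8, effect size 0.98. The same paragraph gives 80% power at two-sided 5% for that difference "between cases (PCOS OSA) and controls (PCOS low risk of OSA"), with 15 and 23 women at a planned 40:60 split.

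The Table 3 caption describes the source contrast as "between people with sleep disorders breathing and healthy controls", which is narrower than the text and the column heading.

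On the control condition, section 6.1 lists "depression and impaired quality of life (QoL") among the associations of PCOS, and section 6.6 repeats that "PCOS is associated with subfertility, depression and anxiety, impaired QoL". On the make-up of the control group, section 5 includes "women with normal ESS and normal Berlin questionnaire (no sleep studies performed"). Section 11 adds: "If the score on either of the questionnaires was abnormal then home-based sleep studies will be arranged". Section 13.5 gives the Berlin questionnaire alone a sensitivity of around 85%.

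Section 13.6 says that the same validation study also contained women with PCOS, but their scores are not reproduced. Section 14.2 plans linear models adjusted for age, BMI, WHR and other factors.

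**The concern.** The reference group behind the planning value is well, whereas the trial's reference group has PCOS. If PCOS has already lowered physical health scores, and OSA acts partly through the same routes, the gap between the two PCOS groups could be smaller than 17.8. Women normal on both questionnaires enter the control group without a sleep study, so undetected OSA there could narrow it further. The caption makes the source look closer to OSA than it is.

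There is little slack: the threshold for 80% power is only about 0.4 points below the planning value. This is the study's only sample size justification. If the true gap were well below 17.8, a null result would say little, and a reader relying on the stated 80% could give it too much weight.

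**Working it through.** **Inputs (section 14.1 and Table 3).** Two-sided alpha 0.05; n1 = 15, n2 = 23; means 75.41 and 57.65; SDs 18.72 and 17.67.

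**Reproducing the plan's figures.**
- Difference: 75.41 − 57.65 = 17.76, printed as 17.8.
- Pooled SD: √[(18.72² + 17.67²)/2] = 18.20, as printed. Weighting by degrees of freedom, √[(140 × 18.72² + 44 × 17.67²)/184] = 18.47.
- Effect size: 17.8/18.2 = 0.98.
- Power of the two-sample t-test: df = 15 + 23 − 2 = 36; critical t = 2.028; non-centrality = (17.8/18.2) × √(15 × 23/38) = 0.978 × 3.013 = 2.947. Power = 0.818.

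The stated 80% is therefore met with a small margin. With the df-weighted SD of 18.47, power is still 0.807.

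**Difference needed for 80% at 15/23.** Solving for power 0.80 gives d = 0.956, that is 0.956 × 18.2 = 17.4 points.

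**Power at other true differences (assumed values; SD 18.2).**

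| True difference | d | Power |
|---|---|---|
| 20 | 1.10 | 90% |
| 17.8 | 0.98 | 82% |
| 15 | 0.82 | 68% |
| 13.35 (75% of 17.8) | 0.73 | 58% |
| 8.9 (50% of 17.8) | 0.49 | 30% |

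**Sensitivity to the SD (assumed values, difference 17.8).** SD 16: power 90%, 80% threshold 15.3 points. SD 20: power 74%, threshold 19.1 points.

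**Do the documents say which row applies?** Some features point to a smaller gap: PCOS is linked to impaired quality of life, and some controls have no sleep study. Others point to a larger one, because the power is for an unadjusted difference, which carries everything that separates the groups:
- Table 1 shows higher weight or BMI with OSA in four of the earlier PCOS studies.
- Category 3 of the Berlin questionnaire is positive for BMI above 30 or hypertension.
- Controls without a sleep study must be normal on the ESS and on the Berlin, which asks about tiredness and fatigue.
- Section 14.2 itself expects imbalance in other predictors.

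A lower control mean does not by itself shrink the difference either. It does so only if OSA costs less in women who already have PCOS, and no figure in the documents bears on that.

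**Undetected OSA in controls.** Assume 15 detected cases, whole-screen sensitivity 85%, and missed women carrying the full deficit. Missed women: 15/0.85 − 15 = 2.65. Difference: 17.8 × (1 − 2.65/23) = 15.75. Power is 72% with SD held at 18.2, or 69% if the control SD is widened for the mixture. With 95% sensitivity and SD held, it is 79%. These inputs are weak. The 85% belongs to the Berlin alone, and either questionnaire triggers a sleep study. At an AHI of 5 to 14 the study's OSA definition needs daytime sleepiness plus gasping, choking or snoring, which most women normal on both questionnaires would not have. Missed cases would mainly be symptom-free women with an AHI of 15 or more, so a full deficit is not the natural assumption.

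**Adjusted models (illustration, nine single-term covariates, df 27, 17.8 points).** Power is 72% if the covariates explain 20% of group membership and none of the outcome, and 89% if they explain 20% of the outcome and none of group membership. The direction is open.

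**The case for a change.** The strongest case for a change is that naming a source does not justify transferring its result. The 17.8 is not offered as a clinically chosen target: the protocol gives a minimal important difference for the PCOSQ (0.5) but none for the WHOQOL-BREF. The same validation study had a PCOS group that Table 3 leaves unused. Section 6.6 criticises earlier work for small samples, so readers of a 38-woman study should know that it is powered only for differences near one SD. The remedy would be cheap: a sentence, a short table and a caption correction.

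Most of this stands as description: the rationale is missing, and a sentence supplying it would have been good practice. What does not stand is the step from a missing rationale to a power claim that is wrong. Section 14.1 already shows that the target is large; it calls 0.98 a large effect and prints both means and SDs, so a reader can see what was borrowed and from whom. The added scenarios would rest on assumed differences. Nor would they protect the reading of a null result, which depends on the estimate and its confidence interval. At SD 18.2 and 15/23 the unadjusted 95% half-width is 2.028 × 18.2 × √(1/15 + 1/23) = 12.25 points, whatever planning value was used.

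**Conclusion.** The observation is accurate, but it calls for no change. The planning difference is borrowed from a contrast that is not specific to PCOS, and the transfer is not argued. The power statement is nonetheless explicit about its condition and correct under it: 82% at 17.8 points, with 80% reached at about 17.4 points (0.96 SD), for an unadjusted t-test at SD 18.2 and 15/23. Power at other gaps runs from 30% at 8.9 points to 90% at 20. The documents contain no WHOQOL-BREF scores for women with PCOS that would place the true gap in that range, so no shortfall against the stated 80% is shown.

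Adding a rationale would leave the sample size, group definitions, analysis and every reported result as they are. The caption wording is a clerical slip: the column heading and the text of 14.1 identify the source group correctly, and the slip does not enter the calculation. This conclusion assumes that the study is reported with effect estimates and confidence intervals, which is how a null finding from 38 women should be read.
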